Follow up phone call at Week 36

Study personnel will call subjects to collect information regarding the status of any ongoing AEs/SAEs or the occurrence of any new AEs/SAEs since last study visit.

EARLY TERMINATION VISIT

If a subject is withdrawn from the study for any reason, including withdrawing informed consent, he/she will be asked to return for an early termination visit within 2 weeks of being withdrawn from the study. Procedures performed at Early Termination Visit will be identical to Week 26 visit.

Treatment of Subjects

Investigational Treatment: Secukinumab (Cosentyx)

Secukinumab (Cosentyx) is a human monoclonal antibody that targets IL-17a and is FDA-approved for the treatment of psoriasis, psoriatic arthritis, and ankylosing spondylitis. Recent literature expanding on the previously poorly understood pathogenesis of NLD has suggested a potential role for IL-17 in the development of this condition. Thus blockade of IL-17 may be a potential therapeutic strategy in patients with NLD

Dosage

Dosage of Secukinumab will be given according to the standard therapy regimen for psoriasis and administered for 24 weeks. Each subject will receive 300mg of Secukinumab by using 2 syringes of 150mg each as a subcutaneous injection at weeks 0,1,2,3,4 then every 4 weeks for a total of 9 doses over 24 weeks. Medication will be administered during scheduled study visits by study personnel.

Use of Co-intervention

Co-medication

A full list of current medication, including over-the counter medicines, will be noted for each subject at time of screening visit and will updated at each visit in their medical chart/report form.

Analgesic Therapy

If a subject develops more than transient pain or the subject's pain increases after starting treatment, they are allowed to start analgesic therapy. In case of NLD-related pain, the subject will be asked to report this at the next visit.

Exacerbation/Intervention

In case exacerbations of NLD lesions occur in the treatment areas and an intervention is required, the investigator may decide to treat with standard therapies not anticipated to decrease size of active areas such as antibiotics. Use of any of the prohibited treatments listed below could that could

confound the efficacy assessment are NOT allowed during the study. If the subject requires treatment with any of the prohibited treatments listed below, the subject should be discontinued from the study treatment will proceed to an early termination visit.

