Any medication or surgical treatment that will be used to treat AEs will be recorded on the electronic case report forms (eCRF).

Prohibited Therapy

The treatments listed below are prohibited for all subjects during the study:

- Any investigational agent
- Any immunosuppressive systemic therapy started within 28 days prior to baseline, including but not limited to oral corticosteroids, adalimumab or other biologic agent, etc.
- Surgical intervention on the treatment areas

Investigational Product/Study Drug

Secukinumab (Cosentyx)

Secukinumab (Cosentyx) is a human monoclonal antibody that targets IL-17a and is FDA approved for the treatment of psoriasis, psoriatic arthritis, and ankylosing spondylitis.

COSENTYX injection is a sterile, preservative-free, clear to slightly opalescent, colorless to slightly yellow solution. COSENTYX is supplied in a single-use Sensoready pen with a 27-gauge fixed ½-inch needle, or a single-use prefilled syringe with a 27-gauge fixed ½-inch needle. The removable cap of the COSENTYX Sensoready pen or prefilled syringe contains natural rubber latex.

Each COSENTYX Sensoready pen or prefilled syringe contains 150 mg of secukinumab formulated in: L-histidine/histidine hydrochloride monohydrate (3.103 mg), L-methionine (0.746 mg), polysorbate 80 (0.2 mg), trehalose dihydrate (75.67 mg), and Sterile Water for Injection, USP, at pH of 5.8.

Secukinumab will be supplied by the sponsor, Novartis, and will be packaged in quantities sufficient to accommodate study design. Each kit will be labeled per local requirements and this label must remain affixed to the kit. Upon receipt, study drug should be stored as specified on the label in their original packaging and kept in a secure location. A temperature log will be maintained for documentation in the research pharmacy. Administration of the study drug will be recorded by study

personnel at scheduled study visits.

Summary of findings from clinical and non-clinical studies

Secukinumab is a recombinant human monoclonal IgG1/κ antibody that binds specifically to IL-17A. It is expressed in a recombinant Chinese Hamster Ovary (CHO) cell line. Secukinumab has a molecular mass of approximately 151 kDa; both heavy chains of secukinumab contain oligosaccharide chains. Please refer to the local label available to you for information regarding the efficacy and safety of this product.

Overview of Study Procedures:
Evaluation Schedule:

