 - (i) clinical signs of inflammation, for example erythematous margins, sensations of itch, pain, dysaesthesia
 - (ii) lesions increasing in size or appearance of new lesions within the last 3 months
 - (iii) ulcerations
4. Subjects must be able to understand and communicate with the investigator and comply with the requirements of the study and must give a written, signed and dated informed consent before any study related activity is performed.

Exclusion Criteria

Eligible subjects will be excluded from participation if they meet any of the following criteria:

1. History of an ongoing, chronic or recurrent infectious disease, or evidence of tuberculosis infection as defined by a positive QuantiFERON TB-Gold test at screening.
2. Are currently pregnant, breastfeeding, or planning to get pregnant during the study.
3. Previous hypersensitivity reaction to secukinumab or to any of the components.
4. History of Inflammatory Bowel Disease (Crohn's Disease or Ulcerative Colitis)
5. Allergy to Latex
6. Currently on any other immunosuppressant systemic medication or within 28 days of baseline visit
7. Women of child-bearing potential, defined as all women physiologically capable of becoming pregnant, unwilling to use effective contraception during the study and for 16 weeks after stopping treatment. Methods of acceptable birth control are listed below under "Women of Childbearing Potential"
8. Subjects with a serum creatinine level exceeding 176.8 $\mu\text{mol/L}$ (2.0 mg/dL)
9. Screening total WBC count $<2,500/\mu\text{L}$, or platelets $<100,000/\mu\text{L}$ or neutrophils $<1,500/\mu\text{L}$ or hemoglobin <8.5 g/dL
10. Known infection with HIV, hepatitis B or hepatitis C at screening or randomization. Patients who are Hepatitis B Core antibody and/or Hep B Surface Antigen positive will be excluded from this study. Patients who are Hepatitis C ab positive will also be excluded from this study.
11. History of lymphoproliferative disease or any known malignancy or history of malignancy of any organ system within the past 5 years (except for non-melanoma skin cancer and carcinoma in situ of the cervix)
12. Are participating in another study using an investigational agent or procedure during participation in this study or within 28 days prior to baseline visit.
13. Plans for administration of live vaccines during the study period or 6 weeks prior to randomization

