14. Any other procedural treatment for NLD with 28 days prior to baseline visit, including phototherapy, surgical intervention, laser therapy, or cryotherapy.
15. Any other active skin disease or condition (e.g., bacterial, fungal or viral infection) that may interfere with assessment of NLD;
16. Underlying condition (including, but not limited to metabolic, hematologic, renal, hepatic, pulmonary, neurologic, endocrine, cardiac, infectious or gastrointestinal) which in the

opinion of the investigator significantly immunocompromises the subject and/or places the subject at unacceptable risk for receiving an immunomodulatory therapy

Women of Childbearing Potential

Women of child-bearing potential, defined as all women physiologically capable of becoming pregnant, unwilling to use effective contraception during the study and for 16 weeks after stopping treatment. Effective contraception is defined as one of the following:

- Combined (estrogen and progestogen containing) hormonal birth control (oral, intravaginal, transdermal) associated with inhibition of ovulation
- Progestogen-only hormonal birth control (oral, injectable, transdermal) associated with inhibition of ovulation
- Bilateral tubal occlusion/ligation
- Intrauterine device (IUD)
- Intrauterine hormone-releasing system (IUS).
- Vasectomized sexual partner(s) (the vasectomized partner should have received medical assessment of the surgical success and is the sole sexual partner of the trial participant).
- True abstinence: Refraining from heterosexual intercourse when this is in line with the preferred and usual lifestyle of the subject (periodic abstinence [e.g., calendar, ovulation, symptothermal, post-ovulation methods] and withdrawal are not acceptable).

B4. POSSIBLE BENEFITS

It is not possible to predict whether you will benefit directly from participation in this study. However, your participation may help others in the future as a result of knowledge gained from the research.

B5. POSSIBLE RISKS AND ANALYSIS OF RISK/BENEFIT RATIO

RISKS AND DISCOMFORTS

Summary of known and potential risks and benefits.

Benefits: there are no FDA-approved treatments for NLD. Subjects enrolled in this study may improve with study treatment. It is not possible to predict whether subjects will benefit directly from participation in this study. However, subject participation may help others in the future as a result of knowledge gained from the research.

Infections

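### As worded, the on-study prohibited list does not expressly bar a systemic immunosuppressant started after baseline, or phototherapy, laser or cryotherapy for NLD, so a subject given one can count as a Week 24 responder

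*Combined protocol and SAP*

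**What the plan says.** The Prohibited Therapy list in B3.A opens with "The treatments listed below are prohibited for all subjects during the study" and has three items. The first is any investigational agent. The second begins "Any immunosuppressive systemic therapy started within 28 days prior to baseline, including but not limited to oral corticosteroids" and goes on to name adalimumab and other biologics. The third is "Surgical intervention on the treatment areas".

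The Exacerbation/Intervention paragraph gives the list its force. Listed treatments that could "confound the efficacy assessment are NOT allowed during the study", and the rule follows: "If the subject requires treatment with any of the prohibited treatments listed below, the subject should be discontinued". The subject then goes to an early termination visit. For a flare in the treatment areas, the same paragraph lets the investigator use standard therapies that are not expected to shrink the active areas, with antibiotics as the example.

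Two exclusion criteria in B3.C cover the same treatments before entry. Item 6 is "Currently on any other immunosuppressant systemic medication or within 28 days of baseline visit". Item 14 is "Any other procedural treatment for NLD with 28 days prior to baseline visit, including phototherapy, surgical intervention, laser therapy, or cryotherapy".

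Under Main Study parameters (B3.B), a responder has an IGA of 0 or 1, or a drop of at least one point from baseline, at Week 24. No condition is placed on other therapy received.

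**The concern.** An on-study ban should reach treatments begun on study. The immunosuppressant item has a window that ends at baseline, so its words repeat exclusion 6 and add almost nothing after the first dose. The procedural item is narrower than exclusion 14, which lists phototherapy, laser and cryotherapy alongside surgery as separate things.

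The wording matters because discontinuation depends on it. If a treatment is not on the list, nothing expressly requires the subject to stop, and the endpoint definition does not ask what else was given. The trial has no control arm, so improvement from an added treatment cannot be told apart from improvement on secukinumab. The Background section itself cites reports of NLD responding to TNF-alpha antagonists, so the plan accepts that other immunosuppressive treatment may move the disease. Any bias in the primary proportion is likely to be upward.

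**Working it through.** **The text set side by side**

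1. *Systemic immunosuppressant.* Before baseline: barred by exclusion 6 and again by the second list item. Started after baseline: no express words in either.
2. *Phototherapy, laser, cryotherapy for NLD.* In the 28 days before baseline: barred by exclusion 14. After baseline: not on the list. Laser or cryotherapy might be argued to be surgical, but exclusion 14 names them apart from surgery. Phototherapy is not surgical on any reading.
3. *Discontinuation.* Tied to the listed treatments, so not expressly triggered by items 1 and 2 after baseline.
4. *Treatment of adverse events.* The section says that medication and surgery used for this are recorded; it adds no restriction.
5. *Analysis.* The Evaluation Schedule records prior and concomitant therapy after baseline at Weeks 1, 2, 3, 4, 8, 12, 16, 20 and 24, which is 9 visits. No analysis rule uses that record.
6. *Early termination.* That visit mirrors Week 26, where the schedule has no IGA. A subject who is discontinued may have no Week 24 score, and no rule says how that subject counts.

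**Size per affected subject**

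The plan gives no sample size calculation, so there is no figure of its own to reproduce.

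- Input: 18 subjects planned (B3.A, Population).
- Lower bound: 0, if the subject would have responded anyway.
- Upper bound: 1/18 = 0.0556, or 5.6 percentage points.
- Assumed example: 9/18 = 50.0% (exact 95% interval 26.0% to 74.0%) becomes 8/18 = 44.4% (21.5% to 69.2%) when one such responder is recounted. The shift is small beside the interval, but it is systematic.
- The step is 1/n, so it grows if fewer are analysed. The protocol mentions 3 completers and 1 early termination for a post-study call. If those four were the whole analysis set (an assumption; the documents do not say so), it would be 1/4 = 25 points.

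**How much added effect is needed**

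The IGA is worded as change from baseline, and the plan does not state the baseline score. Assuming 5 (no change), the threshold is 5 - 1 = 4, which the scale describes as about 25% improvement. On that assumption, a modest added effect is enough.

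**What the existing schedule can support**

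IGA is scheduled at the same 9 post-baseline visits, with gaps of at most 4 weeks. If visits are kept, the last scheduled IGA before any added therapy is at most 4 weeks old.

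**The case against.** The strongest reply is that nobody would read the list this way. It is headed as applying during the study, its examples are open-ended, and an item that only repeats exclusion 6 would be pointless. A site would probably take it as running from 28 days before baseline onward. The flare text also limits the investigator to therapies not expected to shrink lesions, which leaves out phototherapy, laser or an immunosuppressant given for that purpose, and patients are told to contact the unit if the disease progresses. This largely stands: it makes the point a drafting fault and closes the main route. A reader might infer that the plan permits these treatments, or that such a subject would in practice be kept on study. The documents do not support that; they show only that discontinuation is not expressly required.

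The flare text does not, however, address an immunosuppressant given for another condition or for an adverse event, and it carries no counting rule. Even under the widest reading of the ban, the plan does not say how an affected subject enters the primary proportion.

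A second reply is that materiality is unproven: the study is a descriptive pilot, no test or decision threshold hangs on the proportion, and 1/18 is the weight of any single subject. That is fair. It limits the size of the claim, but the proportion is still the primary result.

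A third reply is that counting every exposed subject as a failure would turn a genuine responder who had a short, unrelated steroid course into a non-responder. That also stands, and the fix allows for it.

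**Conclusion.** The point holds as a mis-worded operative rule. Two list items do not expressly cover the on-study treatments they were evidently meant to cover, and no counting rule makes up for it. The exposure that remains is mainly an immunosuppressant for another indication, or treatment by an outside clinician.

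The effect is 0 to 5.6 percentage points per affected subject at n = 18, most likely upward. The frequency is unknown, so no total can be given. A reader might infer that the primary result is materially biased; nothing in the documents shows that any subject would receive such a therapy. The remark that a small added effect suffices rests on the assumed baseline score of 5.

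The textual gap is clear, its practical weight is uncertain, and the repair is cheap enough to be worth making.

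**What to change.** **Reword the two items.** Prohibit any systemic immunosuppressant, and any procedural treatment for NLD (phototherapy, laser, cryotherapy, surgery), from 28 days before baseline through the Week 24 IGA and the post-treatment biopsy, whichever is later. The biopsy is named because the Skin Biopsy text puts it at Week 26 while the schedule ticks Week 24; a window ending at the IGA could leave the histological endpoint uncovered.

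**List every use** from the concomitant-therapy record, with timing, indication, the last IGA before it, and the Week 24 IGA if obtained. Add a prompt for NLD procedures, since the Co-medication text describes a medication list. If the biopsy is taken at Week 26, ask again then, because the schedule has no concomitant-therapy tick at that visit.

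**State how subjects count.** A subject who receives such therapy for NLD before the Week 24 IGA is a non-responder and stays in the denominator. For a brief course for an unrelated condition, report the primary proportion both ways: as observed and as non-response. Define brief in advance.

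**Cost.** Two reworded items, one counting rule, one prompt and a short listing; no new visit or efficacy assessment. The reported proportion may be slightly lower (up to 5.6 points per affected subject at n = 18), and an occasional subject may be discontinued who would otherwise have stayed. Rewording cannot bind an outside clinician; it settles how the subject is handled and counted afterwards.

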Cosentyx may increase the risk of infections. In clinical trials, a higher rate of infections was observed in Cosentyx treated subjects compared to placebo-treated subjects. In placebo-controlled clinical trials in patients with moderate to severe plaque psoriasis, higher rates of common infections such as

nasopharyngitis (11.4% versus 8.6%), upper respiratory tract infection (2.5% versus 0.7%) and mucocutaneous infections with candida (1.2% versus 0.3%) were observed with COSENTYX compared with placebo. A similar increase in risk of infection was seen in placebo-controlled trials in patients with psoriatic arthritis and ankylosing spondylitis. The incidence of some types of infections appeared to be dose-dependent in clinical studies.

We will evaluate patients for tuberculosis (TB) infection prior to initiating treatment with COSENTYX. A positive TB test would lead to exclusion from the trial.

Inflammatory Bowel Disease

Exacerbations of inflammatory bowel disease (IBD), in some cases serious, occurred in COSENTYX treated patients during clinical trials in plaque psoriasis, psoriatic arthritis and ankylosing spondylitis. In addition, new onset inflammatory bowel disease cases occurred in clinical trials with COSENTYX. In an exploratory study in 59 patients with active Crohn's disease, there were trends toward greater disease activity and increased adverse events in the secukinumab group as compared to the placebo group.

Patients will be screened prior to inclusion in trial for a history of IBD. Patients who are treated with Cosentyx should be monitored for signs and symptoms of inflammatory bowel disease.

Hypersensitivity Reaction

Anaphylaxis and cases of urticaria occurred in Cosentyx treated patients in clinical trials. If an anaphylactic or other serious allergic reaction occurs, administration of Cosentyx should be discontinued immediately and appropriate therapy initiated.

Risk of Hypersensitivity in Latex-sensitive Individuals

The removable cap of the Cosentyx Sensoready pen and the Cosentyx prefilled syringe contains natural rubber latex which may cause an allergic reaction in latex-sensitive individuals. The safe use of Cosentyx Sensoready pen or prefilled syringe in latex-sensitive individuals has not been studied.

Vaccinations

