Patients treated with Cosentyx should not receive live vaccines. Prior to initiating therapy with Cosentyx, we will consider completion of all age appropriate immunizations according to current immunization guidelines.

Non-live vaccinations received during a course of Cosentyx may not elicit an immune response sufficient to prevent disease.

Risks listed in the consent form are the following:

Common

- Sore throat and stuffy nose (upper respiratory tract infection, nasopharyngitis),
- Runny nose (rhinitis), diarrhea
- Cold sores (oral herpes)

Rare

- Oral thrush (oral candidiasis),
- signs of low levels of white blood cells, such as fever, sore throat or mouth ulcers due to infections (neutropenia),

- athlete's foot (tinea pedis),
- infection of the external ear (otitis externa),
- discharge from the eye with itching,
- redness and swelling (conjunctivitis),
- itchy rash (urticaria)

Other Risks Related to Study Procedures:

- **Blood Tests:** The risks and discomforts of blood draws
- **Subcutaneous (SC) Injection:** discomfort, infections, and/or pain at the site of the injection.
- **Skin Biopsy:** bleeding, pain, infection, scar

B6. RECRUITMENT AND CONSENT PROCEDURES

Recruitment

Dermatologists and Dermatopathologists from Beth Israel Deaconess Medical Center will be informed using IRB approved recruitment letters of this study and asked to refer eligible patients to our research unit. These letters will explain the purpose of the research, including a brief description of the nature and extent of involvement, and the investigator's email and phone number will be included. A research advertisement will also be posted in the dermatology clinic.

A list of potential subjects will be compiled from all BIDMC Dermatology physicians' patient population using ICD codes for necrobiosis lipoidica diabetorum. These identified patients will be sent recruitment letters informing them of the study and to contact [name] if they are interested.

The study will also be placed on TrialX as well as skinstudies.com, craigslist, twitter and BU quickie jobs. TrialX will use clinicaltrials.gov information; skinstudies.com, craigslist, twitter and BU quickie jobs will use the recruitment flyer and language from the targeted provider email.

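### The risk list that the protocol attributes to the consent form omits inflammatory bowel disease and anaphylaxis, which section B5 names as drug risks, and the bowel monitoring that B5 calls for has no item in the visit schedule

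*Combined protocol and SAP*

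**What the plan says.** Section B5 of the combined protocol and SAP first describes the risks of the drug under separate subheadings.

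- **Inflammatory Bowel Disease:** "Exacerbations of inflammatory bowel disease (IBD), in some cases serious, occurred in COSENTYX treated patients during clinical trials". The same paragraph adds that "new onset inflammatory bowel disease cases occurred in clinical trials with COSENTYX". It says that patients will be screened for a history of IBD before inclusion, and that those treated "should be monitored for signs and symptoms of inflammatory bowel disease".
- **Hypersensitivity Reaction:** this subsection opens by saying that "Anaphylaxis and cases of urticaria occurred in Cosentyx treated patients in clinical trials". The text then states what is to be done if an anaphylactic or other serious allergic reaction occurs.

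Later in B5 comes a list introduced with "Risks listed in the consent form are the following". Under Common it gives upper respiratory infection, "Runny nose (rhinitis), diarrhea" and cold sores. Under Rare it gives oral thrush, neutropenia, athlete's foot, external ear infection, conjunctivitis and urticaria. The risks of blood tests, injections and biopsy follow.

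On safety follow-up, Safety Parameters (B3) has adverse events registered at every visit. The evaluation schedule has a general adverse-event row but no row for IBD. The end of the Immunohistochemistry text in B3 instructs patients to call or visit if they have an adverse event. The Week 36 call asks about ongoing and new adverse events.

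**The concern.** Two parts of the same section disagree about what the drug can do. The descriptive part names two serious risks. The list said to be in the consent form leaves both out, while including minor effects such as athlete's foot. A subject who relied on that list would not learn in writing that IBD or a serious allergic reaction is a known possibility.

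The second part follows from the first. B5 calls for monitoring for IBD, but no procedure in the schedule carries it out by name. General adverse-event questioning can pick up bowel symptoms, and it does so better when staff ask about them and subjects know why they matter. The Sample Size Calculation paragraph describes the trial as a feasibility and tolerability pilot, so safety reporting is part of its purpose. What is at stake is informed consent and the recording of safety events. No statistical quantity depends on it.

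**Working it through.** The plan gives no figure to reproduce, so the check sets the texts side by side and then counts the scheduled contacts.

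**Step 1. Risks described in B5 against the list attributed to the consent form**

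| Risk described in B5 | In the list? | Covered elsewhere? |
|---|---|---|
| Common infections (nasopharyngitis, upper respiratory, candida) | Yes | – |
| IBD, exacerbation | No | Largely, by exclusion 4 (history of IBD) |
| IBD, new onset | No | No; a history exclusion cannot remove it |
| Anaphylaxis or other serious allergic reaction | No | Partly; exclusion 3 covers only a previous reaction to the drug or its components |
| Urticaria | Yes, under Rare | – |
| Latex reaction | No | Largely, by exclusion 5 (latex allergy) |

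The list holds ten drug effects: four under Common and six under Rare, counting the two conjunctivitis lines as one item. Neither IBD nor anaphylaxis is among them. The B5 sentence on hypersensitivity names anaphylaxis and urticaria together, and only urticaria was carried across.

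**Step 2. Where the monitoring for IBD is carried out**

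The evaluation schedule has no IBD item. The general adverse-event row is ticked at baseline and Weeks 1, 2, 3, 4, 8, 12, 16, 20 and 24, and at the Week 36 call: 10 visits + 1 call = 11 contacts. Detection of IBD rests on these contacts and on the general instruction to call or visit.

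**Step 3. The longest interval without a scheduled assessment**

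- Last dose in the schedule: Week 20. The doses at Weeks 0, 1, 2, 3, 4, 8, 12, 16 and 20 make the stated total of nine.
- Last adverse-event assessment at a visit: Week 24.
- Last contact: the Week 36 call.
- Longest interval in the schedule: 36 − 24 = 12 weeks.

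The Week 26 column ticks only suture removal, for those who had a suture. If the statement in Safety Parameters that adverse events are registered at every visit is applied to Week 26, the interval for a subject who attends is 36 − 26 = 10 weeks. The range is therefore 10 to 12 weeks, with 12 the figure in the schedule.

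**The case against.** The strongest reply is that the consent form is not available. The list in B5 may be a summary grouped by frequency, and the form may carry a separate warnings section. Section B6 also has a licensed physician explain the risks before signature and refers to other written information given to subjects. This limits what can be said about the form, but it does not rescue the protocol. B5 presents the list as the risks in the form, so if the form is fuller, the B5 list is wrong and still needs correcting. The oral explanation is described only in general terms and names neither risk.

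A reader might infer several stronger points, which the documents do not support.

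- *Subjects are not told to report these events.* A list of risks is not a reporting instruction, and B3 instructs patients to call or visit for any adverse event. Adverse events are also sought at 11 scheduled contacts, so detection does not depend only on subjects volunteering symptoms.
- *The protocol requires monitoring for both events.* The monitoring sentence concerns IBD only. For anaphylaxis, B5 states an action if it occurs.
- *Listing diarrhea under Common plays down IBD.* Common is a frequency heading, not a grade of severity, and contradicts nothing else in B5. Listing diarrhea could equally prompt subjects to mention it. Late reporting is possible but not shown.
- *Latex is an undisclosed risk to every subject.* B5 confines it to latex-sensitive people, and exclusion 5 excludes latex allergy.
- *Subjects go 16 weeks without assessment.* That is the time from last dose to last contact (36 − 20 = 16). A Week 24 visit with adverse-event assessment, physical examination and blood tests falls within it.

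It is also fair to say that the exclusion of IBD history removes most of the exacerbation risk. New-onset IBD remains.

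**Conclusion.** The point holds as a mismatch within the protocol. The list that B5 attributes to the consent form omits IBD, including new onset, and anaphylaxis or serious allergic reaction, both of which B5 itself describes. On that list, subjects are not told in writing of these known risks. The monitoring for IBD that B5 calls for has no item of its own in the schedule and rests on general adverse-event recording, with 12 weeks (Week 24 to Week 36) in which none is scheduled.

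The omission would apply to all 18 planned subjects. The conclusion assumes that the B5 list reports the form's contents as it says it does. A reader might go further and infer that the form itself is deficient, or that safety data will be incomplete. The first cannot be checked without the form, and the second is not demonstrated given the repeated adverse-event collection. No endpoint, estimate or analysis changes.

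**What to change.** 1. Reconcile the B5 list with the rest of B5 by adding new or worsening IBD, and anaphylaxis or serious allergic reaction. Check the consent form against the corrected list, and amend the form if it shares the omission.
2. Carry out the monitoring that B5 already states by naming bowel symptoms in the existing adverse-event question, at the visits and on the Week 36 call. No new visit or procedure is needed.

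The cost is a wording amendment to the protocol and, if needed, the consent form, together with notification of subjects already enrolled. The protocol already plans a call about side effects to three completers and one subject who ended early (3 + 1 = 4), which offers a ready route for telling those four.
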